### 4.4.7.8 Examination of Subgroups

The primary efficacy endpoint and select secondary efficacy endpoints will be analyzed based on:

- Age (< 65 years of age vs  $\ge 65$  years of age)
- Gender (Male vs Female)
- Race (White vs All Other Races)
- Ethnicity (Hispanic or Latino vs Not Hispanic or Latino)
- Cholestatic liver disease type (PBC or PSC)
- Prescence of IBD (Yes or No)
- IBD Type (CD or UC)
- OCA use at baseline (Yes or No)
- Geographic region (North America vs Europe/Rest of the World)
- Baseline itch severity (moderate/WI-NRS <7 vs severe/WI-NRS ≥7)

- Any improvement in PGI-C (Week 6 for Double-Blind Treatment Period; Week 12 for Open-Label Extension Period [Open-Label Extension Analysis Set only])

The primary and select secondary efficacy endpoints to include the WI-NRS responder analysis will be analyzed for the subgroups using the Full Analysis Set and the Open-Label Extension Analysis Set. Separate summaries will be presented for each subgroup category.

Select safety analysis defined in Section 4.5.3 and 4.5.5 will be analyzed by the following subgroups:

- Cholestatic liver disease type (PBC or PSC)
- Baseline eGFR ( $<90 \text{ vs} \ge 90 \text{ mL/min/}1.73 \text{ m}^2$ )

A summary of subject disposition will also be provided by each subgroup. Demographic and baseline characteristics will be further explored by the stratum factor, cholestatic liver disease type. Summaries by subgroup will only be produced if there are at least 5 subjects in the category of interest for each treatment group. Additional subgroup analyses may be performed post-hoc, as appropriate.

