# 3.4.1.2 Secondary Efficacy Variables

All efficacy assessments will be performed as indicated in the Schedule of Assessments (Appendix A) of the clinical study protocol. Secondary efficacy endpoints include the following:

- Change from baseline in 5-D Itch Scale
- The proportion of subjects with improvement in pruritus as defined by PGI-C
- The proportion of subjects with improvement in pruritus severity from baseline as defined by change in PGI-S
- The proportion of subjects with a reduction in WI-NRS  $\geq 2$  from baseline
- The proportion of subjects with a reduction in WI-NRS  $\geq 3$  from baseline
- The proportion of subjects with a reduction in WI-NRS ≥4 from baseline
- The proportion of subjects with WI-NRS <4

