# **PGI-C**

Subjects will be asked to rate their impression of overall change in pruritus in the past 7 days compared to before they started taking study drug using the PGI-C. The PGI-C is a 7-point scale ranging from "Much Improved" to "Much Worse" and requires approximately 1 minute to complete (Guy 1976). Higher scores indicate less improvement in pruritus. For analysis purposes, subjects that report a change in their itch of "Minimally Improved" or better will be considered as being a responder for "improvement in pruritus" efficacy considerations.

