# 4.2 Analysis Sets

The analysis sets are defined as follows for the Double-Blind Treatment Period:

• Full Analysis Set: All subjects who are randomized and take at least 1 dose of randomized study drug will be included in the Full Analysis Set. Subjects in the Full Analysis Set will be analyzed according to randomized treatment assignment. If a subject is incorrectly stratified (i.e., randomized according to an incorrect stratification), the subject will be analyzed under the randomized treatment for the stratum recorded in the IWRS. All efficacy and PD analyses will be based on the Full Analysis Set.

- Per Protocol Set: The Per Protocol Set is a subset of the Full Analysis Set containing subjects who meet study eligibility requirements and have no protocol deviations that might impact the assessment of efficacy measurements. Subjects will be analyzed according to randomized treatment assignment. The Per Protocol Set will be used for sensitivity analyses relating to efficacy and PD. Protocol deviations that qualify for exclusion from the Per Protocol Set include:
  - Deviations of inclusion/exclusion criteria
  - Non-permitted concomitant medications that may meaningfully impact efficacy outcomes (e.g., receipt of prohibited and/or a rescue medication qualifying as an intercurrent event)
  - Meaningful dosing and/or randomization error(s)
  - Any other important protocol deviation deemed by the Sponsor to warrant exclusion from the Per Protocol set

Any protocol deviations that govern exclusion from the Per Protocol Set will be determined prior to database lock and primary analysis.

- Safety Analysis Set: All subjects who are randomized and take at least 1 dose of randomized study drug will be included in the Safety Analysis Set. Safety analyses will be based upon treatment actually received.
- PK Set: All subjects who receive at least 1 dose of EP547 and provide adequate blood samples for bioanalysis will be included in the PK Set.

Data summaries to be presented on both the Safety Analysis Set and the Full Analysis Set will only be produced on both analysis sets if there is a difference in the population groups.

An Open-Label Extension Analysis Set will be determined as all subjects who complete the Double-Blind Treatment Period and receive at least one dose of study drug in the Open-Label Extension Period and will be used to summarize all available data collected in both the Double-Blind and Open-Label Extension Periods.

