# 4.4 Efficacy and Pharmacodynamic Evaluation

#### 4.4.1 Datasets Analyzed

All efficacy and PD summaries will be based on the Full Analysis Set; select efficacy summaries will also be produced on the Per Protocol Set. In general, the Double-Blind Treatment Period summaries will summarize subjects by treatment group; the Open-Label Extension Period will summarize subjects by randomized treatment from the Double-Blind Treatment Period as well as by all subjects combined. A data listing of subjects excluded from the Full Analysis Set or Per Protocol Set, to include the reason for exclusion, will be presented. The efficacy and PD endpoints will be further evaluated during the Open-Label Extension Period with descriptive statistics for the Open-Label Extension Analysis Set; summaries of change over time will evaluate both change from baseline and change from the initiation of OLE.

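### SAP 4.4.7.8 uses Week 6 PGI-C improvement, a post-randomization outcome, as a by-arm efficacy subgroup; if EP547 affects PGI-C, the arms within its strata are not comparable (minor)

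*SAP*

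**What the plan says.** SAP 4.4.7.8 lists eleven factors for subgroup analysis of efficacy. Ten are demographic or baseline characteristics: age, sex, race, ethnicity, disease type, presence of IBD, IBD type, OCA use at baseline, region and baseline itch severity. The eleventh is "Any improvement in PGI-C (Week 6 for Double-Blind Treatment Period; Week 12 for Open-Label Extension Period", the latter for the Open-Label Extension (OLE) Analysis Set only.

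On what is done within them: "The primary and select secondary efficacy endpoints to include the WI-NRS responder analysis will be analyzed for the subgroups using the Full Analysis Set", and also the OLE set. Each category is summarized separately, subject to the rule that "Summaries by subgroup will only be produced if there are at least 5 subjects in the category of interest for each treatment group".

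On layout, SAP 4.4.1 states that "the Double-Blind Treatment Period summaries will summarize subjects by treatment group" and that "the Open-Label Extension Period will summarize subjects by randomized treatment from the Double-Blind Treatment Period", in the OLE case with a further column over all subjects.

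On the factor itself, the PGI-C text in SAP 3.4.1.2 has subjects "rate their impression of overall change in pruritus in the past 7 days compared to before they started taking study drug", so no pre-treatment value exists. The same section lists as a secondary endpoint "The proportion of subjects with improvement in pruritus as defined by PGI-C", and SAP 4.4.4.2 compares that proportion between arms at Week 6 with a stratified CMH test.

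Protocol 14.11 names demographic and baseline subgroups, allows others of that kind, and leaves further detail to the SAP. SAP 4.7 declares no departure from the protocol.

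**The concern.** Randomization makes the arms comparable within strata fixed before treatment. It gives no such protection within strata defined by something treatment may change. If EP547 moves some subjects from not improved to improved, the improved group on EP547 includes subjects who would not have been improved on placebo. The not-improved group on EP547 is then left with the harder cases. If PGI-C tracks WI-NRS change, as two ratings of the same itch probably do, both strata compare unlike subjects.

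At stake is the reading of one table. Side-by-side arm means for the primary endpoint within PGI-C strata invite a treatment comparison, and the SAP has no caution against making one. If EP547 helps, the table would understate that help in both strata.

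**Working it through.** **Inputs from the documents.** SD of WI-NRS change 2.5 and 26 completers per arm (SAP 4.6). The plan's enrolment figure reproduces: 26 / (1 − 0.10) = 28.9, rounded up to 29 per arm. The point does not depend on it.

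**Assumed inputs (none in the documents).** Placebo improvement rate p0 from 0.3 to 0.7; EP547 rate p1 equal, 10 points higher or 20 points higher; correlation r of 0.5, 0.7 or 0.9 between WI-NRS change and a latent PGI-C score, the two taken as bivariate normal.

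**Formulae.** Let a = z(p) be the normal quantile and φ the normal density. Express the treatment difference as itch reduction on EP547 minus itch reduction on placebo, so that a negative shift is against EP547.
- Improved stratum: 2.5·r·[φ(a1)/p1 − φ(a0)/p0]
- Not-improved stratum: 2.5·r·[φ(a0)/(1 − p0) − φ(a1)/(1 − p1)]

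The true WI-NRS effect does not enter. With p1 = p0 or r = 0, both shifts are zero.

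**Worked example: p0 = 0.5, p1 = 0.7, r = 0.7.** φ(a0) = 0.3989 and φ(a1) = 0.3477.
- Improved: 1.75 × (0.4967 − 0.7979) = −0.53
- Not improved: 1.75 × (0.7979 − 1.1590) = −0.63

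Reversing the direction (p0 = 0.5, p1 = 0.3) gives +0.63 and +0.53, in favour of EP547.

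**Grid, r from 0.5 to 0.9.** The second column is the binomial probability that both strata hold at least 5 of 26 subjects in each arm, that is, 5 to 21 improved in both.

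| Placebo → EP547 improved | Both strata reported | Shift, improved | Shift, not improved |
|---|---|---|---|
| 30% → 40% | 0.92 | −0.24 to −0.43 | −0.18 to −0.33 |
| 40% → 50% | 0.99 | −0.21 to −0.38 | −0.19 to −0.35 |
| 50% → 60% | 0.99 | −0.19 to −0.35 | −0.21 to −0.38 |
| 60% → 70% | 0.92 | −0.18 to −0.33 | −0.24 to −0.43 |
| 70% → 80% | 0.57 | −0.18 to −0.33 | −0.30 to −0.54 |
| 30% → 50% | 0.93 | −0.45 to −0.81 | −0.38 to −0.68 |
| 40% → 60% | 0.99 | −0.40 to −0.72 | −0.40 to −0.72 |
| 50% → 70% | 0.93 | −0.38 to −0.68 | −0.45 to −0.81 |
| 60% → 80% | 0.61 | −0.37 to −0.66 | −0.54 to −0.98 |
| 70% → 90% | 0.10 | −0.38 to −0.68 | −0.75 to −1.34 |

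Keeping only rows with probability of at least 0.9, the shift is 0.18 to 0.43 points for a 10-point gap and 0.38 to 0.81 for a 20-point gap.

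**Check by simulation (1,000,000 per arm).** With improvement raised from 40% to 60%, no WI-NRS effect and r = 0.7, false differences of 0.56 and 0.55 against EP547 appeared in the two strata; the formula gives 0.56. With an assumed true effect of 2.0 acting on PGI-C only through itch, r = 0.7 and placebo rate 50%, the EP547 rate became 71% and the within-stratum effects fell to 1.44 (improved) and 1.32 (not improved).

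**Sampling error at 50% versus 70% improved.** Expected counts are 13 versus 18 (improved) and 13 versus 8 (not improved). The 95% half-width is t × SD × √(1/m0 + 1/m1), with the within-stratum SD taken as 2.0 to 2.5.
- Improved, 29 df: 2.045 × SD × √(1/13 + 1/18) = 1.49 to 1.86
- Not improved, 19 df: 2.093 × SD × √(1/13 + 1/8) = 1.88 to 2.35

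So it is about 1.5 to 2.4 points, wider than any shift retained above.

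**The case against.** The strongest defence is that this is a descriptive display. The SAP specifies no model, contrast or p-value within the PGI-C strata, the item's own label shows that it is a response, noise exceeds bias, and when EP547 improves PGI-C the shift works against it and so cannot manufacture benefit. Protocol 14.11 leaves details to the SAP, and SAP 4.1.1 plans an overall column in tables generally. Most of this stands, and it is why the point is minor. It does not remove the point. The by-arm columns are still planned, SAP 4.4.7.8 says the endpoints will be analyzed, and no text restricts this factor to a pooled or non-comparative use.

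Three stronger readings are tempting but unsupported.
- A reader might infer that any PGI-C effect biases against EP547. The direction depends on whether EP547 raises or lowers the improvement rate.
- A reader might infer distortions above a point. The 1.34 arises only at 70% versus 90% improved with r = 0.9, where about 2.6 of 26 EP547 subjects are expected in the not-improved stratum and the 5-per-arm rule lets both strata be reported only about 10% of the time.
- A reader might infer that the Week 12 split carries the same bias, because the OLE set "will be used to summarize all available data collected in both the Double-Blind and Open-Label Extension Periods". But all subjects then receive EP547, membership already requires completing double-blind treatment, summaries are descriptive and a column over all subjects is planned. There is no concurrent placebo contrast. Only the columns by randomized arm share the selection.

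**Conclusion.** The concern holds in a narrow form. SAP 4.4.7.8 would split the primary endpoint by a Week 6 outcome and show it by arm. Those within-stratum comparisons are not protected by randomization if EP547 affects PGI-C and PGI-C correlates with WI-NRS change. In settings where both strata are likely to be reported, the illustrative shift is 0.18 to 0.81 points for gaps of 10 to 20 points in improvement rates. Those sizes rest on assumed rates, assumed correlations and a bivariate normal model; only the SD and the number per arm come from the SAP.

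The primary MMRM, its type I error and the sample size are untouched. The PGI-C item also falls outside the demographic and baseline scope of Protocol 14.11 without an entry in SAP 4.7, which is a documentation gap. Severity: minor.

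**What to change.** Delete the PGI-C item from the efficacy subgroup list in SAP 4.4.7.8. If the relation between the two scales is of interest, replace it with a sentence such as:

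*WI-NRS change will be summarized descriptively by PGI-C category at the same visit (Week 6; Week 12 for the Open-Label Extension Analysis Set), pooled over randomized arms, with no by-arm columns and no between-arm contrast.*

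Record any retained PGI-C summary in SAP 4.7 as an addition to the subgroups of Protocol 14.11.

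The cost is one deleted bullet and, optionally, one sentence, one pooled table and one line in SAP 4.7. No new data are needed. What is lost is a by-arm table within PGI-C responder strata.

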#### 4.4.8 EP547 Plasma Concentrations

Raw plasma concentration values will be summarized for the PK Set by treatment group and sampling time point in the Double-Blind Treatment Period using descriptive statistics, to include the geometric mean and CV (%). The geometric CV is calculated as  $100*sqrt[exp(\sigma^2)-1]$ , where  $\sigma^2$  is the variance of the log-transformed data. For summaries of plasma concentrations, BLQ values will be set to missing. The number and percentage of subjects with BLQ values will be summarized by time point and treatment group.

# 4.4.9 Pharmacokinetic Analysis

Pharmacokinetic analysis will be based on analysis of the EP547 concentration data as outlined in Section 4.4.8.

# 4.5 Safety Evaluation

Safety analyses during the Double-Blind Treatment Period will be carried out for the Safety Analysis Set, to include all subjects who receive at least one dose of study drug. Safety analyses during the Double-Blind Treatment Period and Open-Label Extension Period will be summarized for the Open-Label Extension Analysis Set, to include all subjects who receive at least one dose of study drug during open-label participation. Safety data will be summarized separately for the Double-Blind Treatment Period and Open-Label Extension Period by randomized Double-Blind treatment received; a summary of all subjects combined within each study treatment period will also be provided. Subjects who do not complete the study, for whatever reason, will have all available data up until the time of termination included in the analysis. For safety analysis presented by study visit, the baseline value will be defined as described in Section 4.1.2 to include a Change from Baseline and Change from Initiation of OLE assessment.

### 4.5.1 Extent of Exposure

Extent of exposure to study treatment will be summarized by treatment group separately for each study treatment period as well as over the entire study participation. The duration of exposure will be presented in days and calculated as the date of last dose of study drug of the respective study treatment period minus the date of first dose of study drug of the respective study treatment period, plus one. For the purposes of defining the start of the Open-Label Extension Period, the on-site dose from the Week 6 Study Drug Administration (On-site) eCRF will be considered the start of OLE dosing for the duration of exposure calculation in the Open-Label Extension Period. The Open-Label Extension Period summary will also include a summary of duration of exposure across all study participation (both study treatment periods).

As dosing includes receipt of a 25 mg and 75 mg tablet for each daily dose totaling 100 mg of study drug, the total number of tablets received in each study treatment period will be determined based on treatment period dosing ranges as described in Section 4.5.2 (Treatment Compliance) and dosing will be based on the number of tablets received with the following derivation:

- Subjects reporting an even number of tablets will have their total dose received (mg) calculated as: (total tablets taken during study treatment period divided by 2) multiplied by 100.
- Subjects reporting an odd number of tablets (i.e., there was an incomplete dosing day) will have their total dose received (mg) calculated as: (the floor of [total tablets taken during study treatment period divided by 2] multiplied by 100) + 25 mg.

Duration of exposure and total dose received (mg) will be summarized using descriptive statistics. The Open-Label Extension Period summary will also include a summary of total dose received for EP547 across both study treatment periods for those randomized to EP547.

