The Double-Blind Treatment Period will consist of five study visits (Visits 2, 3, 4, 5, and 6 [Day 1 and Weeks 1, 2, 3, and 6]). During this period, all subjects who meet eligibility requirements will be enrolled into the study and randomized to receive double-blind, PO, QD 100 mg doses of EP547 or placebo for 6 weeks beginning on Visit 2 (Day 1). Visit 2 (Day 1) will not have a visit window; however, for the decentralized model, enrollment/randomization and the first dose of study drug may be separated by up to 10 additional calendar days to allow for home delivery of study drug. When enrollment/randomization and first dose of study drug are on separate days, the first dose of study drug is considered Day 1. All other visits in the Double-Blind Treatment Period will have a visit window of ±3 days.

For the hybrid model, Visits 1, 2, 6, and 8 (Screening, Day 1, Week 6, and Week 12) and early termination (if applicable) must be completed at the study site. All other study visits may be conducted remotely, where allowed per regulatory/local requirements. For the decentralized model, all visits will be conducted remotely.

For remote visits for both the hybrid and decentralized models, the home health nurse visit at the subject's home or work and the telemedicine visit with the study site staff for a given study visit may be conducted on different days but must be within the allowable visit window. The home health nurse will complete the study assessments that the site is physically unable to complete remotely (e.g., blood and lab sample collection, vital signs, electrocardiograms [ECGs]); the site will complete all other study assessments remotely during the telemedicine visit.

The Open-Label Extension Period will consist of two study visits (Visit 7 [Week 9] and Visit 8 [Week 12]). During this period, all subjects who complete the Double-Blind Treatment Period and are still receiving study drug will receive open-label 100 mg doses of EP547. Visit 7 and Visit 8 will have a visit window of ±3 days.

Any subject who completes the Open-Label Extension Period or discontinues study drug (EP547 or placebo) early will complete a Follow-Up Visit (Visit 9) approximately 2 weeks (±3 days) after the last dose of study drug.

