- Within the Open-Label Extension Period, analysis of Week 7 will be the first 7 days after the nominal Week 6 visit date or start date of open-label dosing, whichever is later; for subjects who participate in the decentralized model, there may be a gap between the nominal Week 6 visit and open-label dosing due to drug shipment considerations. Subsequent analysis visits will be counted using the next 7 days. The Week 6 WI-NRS score will be used as the Initiation of OLE score.

The Safety Follow-up Period will be anchored to the nominal Week 12 visit date. Week 13 will be the first 7 days after the nominal Week 12 visit date and Week 14 will be derived using the next 7 days.

For subjects who early terminate during the Double-Blind Treatment Period, the subject's first day of dosing (i.e., study day 1) will be the anchor date for weekly analysis visit derivations. Week 1 will be study days 2 through 8 and subsequent weekly analysis visits will be the next 7 days, deriving all applicable analysis visits until early termination.

The following additional general considerations will be applied in deriving the weekly WI-NRS scores:

- No WI-NRS daily score is to be utilized in more than one analysis visit derivation.
- For weeks where 7 calendar days are available for a given week, there must be 4 non-missing daily scores to compute the weekly score; if more than 3 daily scores are missing, the weekly score is considered missing.

• For weeks where less than 7 calendar days are available for a given week due to visit anchoring rules, at least 57% of the daily scores for the available calendar days must be reported, maintaining the same rate of reported scores as seen for a full week (i.e., 4 out of 7 days). If 6 calendar days are available for a given week, 4 non-missing daily scores are required. If 4 or 5 calendar days are available for a given week, 3 non-missing daily scores are required. If less than 4 calendar days are available for a given week, the weekly score will be considered missing.

A bi-weekly WI-NRS score will be calculated for exploratory analysis. The average WI-NRS score using the daily values from the 14 days before the first dose of study drug (including the WI-NRS score captured on the study day 1 of dosing) will serve as the baseline bi-weekly score.

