# 4.5.2 Measurements of Treatment Compliance

Compliance to the study treatment regimen will be summarized by treatment group, separately for each study treatment period as well as over the entire study participation. Compliance will be determined based on tablet count entries made on the Study Drug Dispensing and Accountability eCRF pages. Expected dosing will be based on the onsite dosing administration:

- The expected tablet dosing for Double-Blind Treatment Period is considered to be the on-site dose from Day 1 to the Treatment Completion or Treatment Discontinuation Date on the End of Treatment (Double-Blind eCRF), plus 1. The number of dosing days is then multiplied by two to account for two tablets of EP-547 or placebo taken each day.
- The expected tablet dosing for Open-Label Extension Period is considered to be the on-site dose from the Week 6 Study Drug Administration (On-site) eCRF to the Treatment Completion or Treatment Discontinuation Date on the End of Treatment (Open-Label eCRF), plus 1. The number of dosing days is then multiplied by two to account for two tablets of EP-547 taken each day.

The actual number of doses (tablets) received will be determined based on the number of tablets taken reported on the Study Drug Dispensing and Accountability eCRF. The number of tablets taken in the Double-Blind Treatment Period and Open-Label Extension Period will be assessed based on the defined treatment period windows (using the date ranges calculated in the expected dosing derivation) and the kit dispense dates.

Treatment compliance will then be calculated as the actual number of tablets taken divided by the expected number of tablets taken, multiplied by 100 for each treatment period and overall.

The number and percentage of subjects who are < 80% compliant and  $\ge 80\%$  compliant within each treatment group will be summarized separately for each study treatment period, as well as for overall study participation.

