#### 4.5.3 Adverse Events

Treatment-emergent adverse events are defined as those AEs with onset after the first dose of study drug or existing events that worsened after the first dose during the study. Treatment-emergent AEs will be summarized by treatment group separately for each study treatment period and overall, within each study treatment period. An overall TEAE summary, incidence of TEAEs by system organ class and preferred term, and summary of the most frequently-occurring TEAEs will also be presented for both periods combined (i.e., overall study) for the Safety Analysis Set and the Open-Label Extension Analysis Set. Adverse events will be considered treatment-emergent relative to the study treatment period where the onset of the AE occurred; any TEAE that begins in the Double-Blind Treatment Period will be considered treatment-emergent in the Double-Blind Treatment Period only. The same logic is to be applied to the Open-Label Extension assessment; the Week 6 Study Drug Administration (On-site) entry will be considered the start of Open-Label Extension dosing for assessing treatmentemergence. Events reported with a partial onset date (e.g., month and year are reported but the day is missing) will be considered to be treatment-emergent in both treatment periods if it cannot be confirmed that the event onset was prior to the first dose of study drug for a specific treatment period based on the available date entries. Events with date and time present will be compared against the treatment start date and time to determine treatment-emergence.

Verbatim terms on case report forms will be mapped to preferred terms and system organ classes using MedDRA, version 25.0.

Summaries that are displayed by system organ class and preferred terms will be ordered by descending incidence of system organ class and preferred term within each system organ class. Summaries displayed by preferred term only will be ordered by descending incidence of preferred term. Inclusion criteria assessments for frequency-related summaries will be made separately for each study treatment period and study overall. Summaries of the following types will be presented:

- Overall summary of number of unique TEAEs and treatment-emergent SAEs and subject incidence of TEAEs meeting various criteria;
- Subject incidence of TEAEs by MedDRA system organ class and preferred term;

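### The SAP ties open-label start to a Week 6 on-site entry for exposure, compliance and adverse events, which does not fit its own allowance for a later home start in the decentralized model

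*SAP*

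**What the plan says.** Three safety sections of the SAP start the open-label period at the same record.

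- SAP 4.5.1 (exposure) first gives a general formula: last dose in the period minus first dose in the period, plus one. It then overrides this for the open-label period: "the on-site dose from the Week 6 Study Drug Administration (On-site) eCRF will be considered the start of OLE dosing".
- SAP 4.5.2 (compliance) counts expected open-label days from the "on-site dose from the Week 6 Study Drug Administration (On-site) eCRF to the Treatment Completion or Treatment Discontinuation Date", plus one, at two tablets a day.
- SAP 4.5.3 (adverse events) says that "the Week 6 Study Drug Administration (On-site) entry will be considered the start of Open-Label Extension dosing" when treatment emergence is judged.

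None of the three has a branch for the decentralized model, of which SAP 3.1 says: "For the decentralized model, all visits will be conducted remotely".

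SAP 3.4.1.1 treats the same moment differently. It says that "for subjects who participate in the decentralized model, there may be a gap between the nominal Week 6 visit and open-label dosing", because of drug shipment, and defines Week 7 of WI-NRS as "the first 7 days after the nominal Week 6 visit date or start date of open-label dosing, whichever is later".

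The Protocol (section 9.4.2.5) has open-label drug dispensed and taken at Visit 6. Its schedule of assessments has a courier dispense drug for remote visits. It gives no delivery allowance at Week 6.

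**The concern.** The SAP expects that some decentralized subjects will take their first open-label dose some days after the Week 6 visit. It corrects for this in the efficacy derivation but not in the exposure, compliance or adverse event derivations. A programmer who follows 4.5.1 to 4.5.3 literally has no on-site dose to use for a subject whose visits are all remote, and may fall back on the visit date.

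At stake is the content of the open-label safety tables. An adverse event with onset in the gap could be tabulated as open-label-emergent before any open-label dose. For a subject randomized to placebo, that is before any EP547. SAP 4.5 presents open-label safety by randomized arm, so the event would appear in the former-placebo column as if it arose on EP547. A subject who took every available open-label dose could also be classed as less than 80% compliant.

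**Working it through.** **Step 1: the definitions side by side**

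| SAP section | Purpose | Open-label start | Allows for a gap? |
|---|---|---|---|
| 3.4.1.1 | WI-NRS weeks | Later of Week 6 visit and open-label dosing start | Yes |
| 4.5.1 | Exposure | Week 6 on-site entry | No |
| 4.5.2 | Expected tablets | Week 6 on-site entry | No |
| 4.5.3 | Treatment emergence | Week 6 on-site entry | No |

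**Step 2: what the on-site entry could hold for a home dose.** The documents do not say.

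1. Nothing, because no dose was taken at a site. The start date is then undefined, and so are exposure, expected tablets and open-label emergence.
2. The Week 6 visit date. All three derivations are then wrong by the length of the gap.
3. The actual home dose date. There is then no error.

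**Step 3: size under case 2.** The plan states no figure here, so there is none to reproduce. Inputs:

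- Planned open-label period: Day 43 to Day 85 (SAP Table 2), so 85 − 43 + 1 = 43 days and 2 × 43 = 86 tablets.
- Compliance = tablets taken / tablets expected × 100, with a cut at 80% (SAP 4.5.2).
- Gap g in days: assumed. The only delivery allowance that the documents quantify is up to 10 days between randomization and first dose (Protocol 9.4.2.1). It does not apply to Week 6 and serves only as the upper end of the range in the table.
- Every available open-label dose is taken, and no other tablets are counted in the period.

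With the end fixed at Day 85, true exposure is 43 − g days, counted exposure is 43 days, and compliance is 2(43 − g)/86.

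| g | True days | Counted days | Exposure overstated | Tablets taken / expected | Compliance |
|---|---|---|---|---|---|
| 0 | 43 | 43 | 0% | 86/86 | 100% |
| 3 | 40 | 43 | 3/40 = 7.5% | 80/86 | 93.0% |
| 7 | 36 | 43 | 7/36 = 19.4% | 72/86 | 83.7% |
| 8 | 35 | 43 | 8/35 = 22.9% | 70/86 | 81.4% |
| 9 | 34 | 43 | 9/34 = 26.5% | 68/86 | 79.1% |
| 10 | 33 | 43 | 10/33 = 30.3% | 66/86 | 76.7% |

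A subject with no missed available dose falls below 80% from a 9-day gap.

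**Step 4: the other end-date assumption.** If the end moves later by g, 86 tablets are taken and 2(43 + g) are expected. At g = 10 this is 86/106 = 81.1%; at g = 11 it is 86/108 = 79.6%. The 80% cut is then crossed only from 11 days.

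**Step 5: with the actual first open-label dose as start.** With the end at Day 85, g = 3 gives 40 days and 80/80 tablets, and g = 10 gives 33 days and 66/66 tablets. Compliance is 100% in both, and no event in the gap is open-label-emergent.

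**The case against.** The strongest reply is that 4.5.1 to 4.5.3 name a dosing record, not a visit date. SAP 4.5.3 compares events with a treatment start date and time, and the general formula in 4.5.1 uses the first dose of the period. The words in brackets may be only a form label. SAP 4.5.2 also applies an on-site Day 1 dose to every subject in the double-blind rule, and SAP 3.1 describes the decentralized model as having a virtual site. If the form holds the actual first dose, it could even be the source of the date that 3.4.1.1 uses, and all four sections would agree.

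This stands in part. A reader might infer that exposure, compliance and event attribution are wrong for decentralized subjects as a group. The documents do not support that. It would need a decentralized subject, an actual gap (the SAP says only that there may be one) and a form that holds the visit date. The documents also give neither the number of decentralized subjects nor a Week 6 gap length, so no study-level effect can be stated.

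The reply does not remove the point. The SAP nowhere says that the form records home doses, and the three sections replace the general first-dose definition with an entry described as on-site. The parallel Day 1 wording shows that the same clarification is needed twice.

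The reply is also right that the consequences are limited. The tables are descriptive, and SAP 4.5.3 provides the main summaries of treatment-emergent events for both periods combined, so gap events are not lost.

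**Conclusion.** The point holds in conditional form. SAP 4.5.1, 4.5.2 and 4.5.3 are inconsistent with 3.4.1.1 on when open-label treatment starts for decentralized subjects who have a gap after Week 6. The start is undefined if there is no on-site entry, too early by the gap if the entry carries the visit date, and correct if it holds the home dose date. The documents do not settle which applies.

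The figures in the working illustrate the visit-date case only. They rest on an assumed gap, the planned 43 days and no missed available dose, and the gap at which compliance drops below 80% depends on whether the end date moves.

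Two further inferences go too far. One is that subjects are off all study drug during the gap: the documents establish only that open-label dosing has not begun. The other is that the efficacy result is at risk: the primary endpoint lies in the double-blind period, and the open-label WI-NRS weeks already allow for the gap. Hybrid subjects are unaffected because their Week 6 visit must be at the site. This is a minor point, confined to the open-label exposure, compliance and adverse event tables.

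**What to change.** - In SAP 4.5.1, 4.5.2 and 4.5.3, define open-label start as the actual date and time of the first open-label dose, wherever it is taken, consistent with 3.4.1.1. Name the record that supplies this for home doses.
- In 4.5.3, state that events with onset before that dose are not open-label-emergent, and say where gap events are reported. Either the double-blind period or a separate line is a reasonable convention; the choice should be fixed before unblinding.
- In 4.5.2, apply the same wording to the on-site Day 1 dose in the double-blind rule.

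The cost is a few sentences in the SAP and one derived date, which 3.4.1.1 already requires. Nothing changes in trial conduct.
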